4.5.1. Reasons for Discontinuation and Individual Stopping Rules

Individual Subjects will be discontinued by the Investigator if they meet any of the stopping rules described below:

1. A significant febrile reaction defined as \geq Grade 2 fever (>39.0 °C) associated with systemic symptomatology (eg, body aches, malaise, nausea) within 24 hours following administration of IP.
2. An absolute decrease in predicted FEV1 of at least 25% compared to the baseline value (defined as the average of the Day -1 and Day 1 pre-dose values) during the 5-week treatment period in Part B or through Day 11 (1 week post-5th dose) in Part D that cannot be explained, in the opinion of the PI, by the underlying disease of CF and that is confirmed on 2 separate occasions at least 3 days apart
3. A suspected moderate to severe allergic/hypersensitivity reaction, including but not limited to anaphylaxis, generalized rash, edema or bronchospasm possibly related to drug treatment
4. Deterioration of liver function as explained below and in Section 8.1.4.1
 - a. Elevation of ALT or AST to >5 x ULN in a subject regardless of baseline value
 - b. Elevation of ALT or AST to >3 x ULN in a subject with a normal baseline or elevation of >3 x ULN from the subject's actual baseline if not normal, with the

appearance of fatigue, nausea, vomiting, right upper quadrant pain or tenderness, fever, rash, and/or eosinophilia (>5%).

c. Elevation of ALT or AST to >3x ULN in a subject with a normal baseline or elevation of >3x ULN from the subject's actual baseline if not normal, and total bilirubin >2x ULN or INR >1.5.

If any of the above criteria is met by a Part B or Part D subject who has not completed dosing with IP, treatment must be interrupted immediately and the Medical Monitor notified of this action.

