8.1.8.1. Allergic/Hypersensitivity Reactions

A suspected moderate to severe allergic/hypersensitivity reaction, including but not limited to anaphylaxis, generalized rash, edema or bronchospasm deemed possibly related to study drug is an AESI for MRT5005. The study site should report the occurrence of such a reaction to the

Sponsor within 24 hours of their first knowledge of the event and record the details of the event on the AE CRF in the EDC system.

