## **2.7 Dose Group and Study Stopping Criteria and Unblinding**

Investigational product administration will be halted for all subjects in a dose group, as well as any subjects in an ongoing higher dose group if any of the following stopping criteria are met:

- a. Two subjects in a dose group experience a significant febrile reaction (defined as  $\geq$  Grade 2 fever [ $>39.0^{\circ}\text{C}$ ] associated with systemic symptomatology [eg, body aches, malaise, nausea]) within 24 hours following administration of IP.
- b. Two subjects in a dose group experience a suspected moderate to severe allergic/hypersensitivity reaction, including but not limited to anaphylaxis, generalized rash, edema or bronchospasm possibly related to drug treatment.

Investigational product administration will be halted for all subjects in Part D if the following stopping criterion is met:

- a. Three subjects experience Grade 1 fevers (38.0 to  $39.0^{\circ}\text{C}$ ) associated with systemic symptomatology (eg, body aches, malaise, nausea) onset within 24 hours following administration of IP on  $\geq 3$  separate occasions.

Investigational product administration will be halted for all subjects if any of the following stopping criteria are met:

- a. A subject experiences a Grade 4, life-threatening treatment-emergent AE or death that is considered probably or definitely related to investigational product by the Investigator.
- b. Two or more subjects in a dose group experience 1 or more moderate or severe pulmonary exacerbations during the 5-week treatment period in part B or through Day 11 (1 week post-5th dose) in Part D.
- c. Two or more subjects in a dose group experience a decrease in predicted FEV1 of at least 25 % compared to the baseline value (defined as the average of the Day -1 and Day 1 pre-dose values) during the 5-week treatment period in Part B or through Day 11 (1 week post-5th dose) in Part D that cannot be explained, in the opinion of the PI, by the underlying disease of CF and that is confirmed on 2 separate occasions at least 3 days apart.
- d. Two or more subjects in the study experience a suspected serious allergic/hypersensitivity reaction, including but not limited to anaphylaxis, generalized rash or bronchospasm likely to be related to drug treatment.
- e. Two or more subjects in a dose group experience a deterioration in liver function, as detailed below:

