### 9.3 Adverse Events

Adverse events will be coded using the Medical Dictionary for Regulatory Activities (MedDRA) Version 23.1 to identify the system organ class and preferred term.

Treatment-emergent AEs are defined as events that are newly reported or reported to worsen in severity after the start of treatment. Adverse events that occur after the treatment start date, occur on the treatment start date with a time that is equal to or after treatment start time, or that have a missing AE start date will be categorized as treatment-emergent. Treatment-emergent AEs will be summarized for the safety analysis set.

For summaries of TEAEs by time interval, the categorizations for Part A will be: Overall, Study Day 1, 1 < Study Day ≤ 7, 1 ≤ Study Day ≤ 29, and Study Day > 29. The categorizations for Part B will be: Overall, Study Day 1, 1 < Study Day ≤ 7, 1 ≤ Study Day ≤ 36, 1 ≤ Study Day ≤ 57, and Study Day > 57. The categorizations for Part D will be: Overall, Study Day 1, 1 < Study Day ≤ 5, 1 ≤ Study Day ≤ 11, 1 ≤ Study Day ≤ 32, and Study Day > 32. The categorizations for the study overall will be: Overall, through 1 month post-dose (Day 29, Day 57, and Day 32 for Part A, Part B, and Part D, respectively), after 1 month post-dose (> Day 29, > Day 57, and > Day 32 for Part A, Part B, and Part D, respectively). Any TEAE with a completely missing start date will not be categorized into a specific time interval, but will be included in the Overall category.

Any dose limiting toxicities identified will be addressed in the clinical study report (CSR).

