Treatment-emergent febrile reactions and hypersensitivity reactions will be presented as a count of febrile reactions, febrile reactions by severity, hypersensitivity reactions, and hypersensitivity reactions by severity. Additionally, the table will reflect the count and percentage of subjects experiencing the following: any febrile reaction, any febrile reaction by severity, any hypersensitivity reaction, and any hypersensitivity reaction by severity. The summary will be for all subjects in the safety analysis set by dose group for each study part. In addition, the summary of treatment-emergent febrile reactions and hypersensitivity reactions will be presented for all subjects in the safety analysis set for the study overall by pooled treatment group. Febrile reactions will be identified based on a preferred term of body temperature increased or preferred term of pyrexia within the 24 hours after completion of

nebulization on any dosing day with at least one other systemic symptom reported as a preferred term of headache, arthralgia, myalgia, fatigue, chills, nausea, or vomiting within the 24 hours after completion of nebulization on any dosing day. Severity grade for febrile reactions will be based on the maximum severity of the preferred terms comprising the febrile reaction. Hypersensitivity reactions will be identified based on a preferred term of hypersensitivity within the 24 hours after completion of nebulization on any dosing day.

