Adverse events leading to withdrawal from treatment, AEs resulting in death, pulmonary exacerbations (investigator and protocol-defined), adverse events of special interest, and SAEs will be presented in data listings for subjects in the safety analysis set. Adverse events of pyrexia or body temperature increased during nebulization or within the 24 hours after completion of nebulization on any dosing day will also be listed for subjects in the safety analysis set. This listing will include all adverse events that occurred during nebulization or within the 24 hours after completion of nebulization for subjects that had an adverse event of pyrexia or body temperature increased during nebulization or within the 24 hours after completion of nebulization on any dosing day. All adverse events that occurred during nebulization or within the 24 hours after completion of nebulization will also be listed for subjects in the safety analysis set. Febrile reactions and hypersensitivity reactions within the 24 hours after completion of nebulization on any dosing day will also be listed for subjects in the safety analysis set. This listing will include all adverse events that meet the specified febrile reaction or hypersensitivity criteria that occurred within the 24 hours after completion of nebulization for subjects that had a febrile reaction or hypersensitivity reaction within the 24 hours after completion of nebulization on any dosing day.

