**Notes:**

1) **AE\_TAM\_F\_X** will be produced for each study part.

Table 14.3.2.5 (AE\_TAO\_F\_O)  
Summary of Treatment-Emergent Febrile Reactions in First 24 Hours After Completion of Nebulization by Preferred Term  
Population: Safety Analysis Set

	Pooled MRT5005 N=xx n (%)	Pooled Placebo N=xx n (%)
Number of Febrile Reactions Reported	xx	xx
Number of Subjects with Any Febrile Reactions Reported [1]	xx (xx.x)	xx (xx.x)
Number of Febrile Reactions by Severity [2]		
Mild	xx	xx
Moderate	xx	xx
Severe	xx	xx
Number of Subjects with Febrile Reactions by Maximum Severity [3]		
Mild	xx (xx.x)	xx (xx.x)
Moderate	xx (xx.x)	xx (xx.x)
Severe	xx (xx.x)	xx (xx.x)

[1] AE\_F05

[2] AE\_F17c

[3] AE\_F07a

Note: AE\_F17a

Listing Source: AE\_LAK\_F\_X

Table 14.3.2.7 (AE\_TAO\_F\_O)  
Summary of Treatment-Emergent Hypersensitivity Reactions in First 24 Hours After Completion of Nebulization by Preferred Term  
Population: Safety Analysis Set

	Pooled MRT5005 N=xx n (%)	Pooled Placebo N=xx n (%)
Number of Hypersensitivity Reactions Reported	xx	xx
Number of Subjects with Any Hypersensitivity Reactions Reported [1]	xx (xx.x)	xx (xx.x)
Number of Hypersensitivity Reactions by Severity		
Mild	xx	xx
Moderate	xx	xx
Severe	xx	xx
Number of Subjects with Hypersensitivity Reactions by Maximum Severity [2]		
Mild	xx (xx.x)	xx (xx.x)
Moderate	xx (xx.x)	xx (xx.x)
Severe	xx (xx.x)	xx (xx.x)

[1] AE\_F05

[2] AE\_F07b

Note: AE\_F17b

Listing Source: AE\_LAK\_F\_X

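### The hypersensitivity tables count one preferred term after nebulization ends; the protocol's AESI overlaps with this but differs, the source listing's note conflicts on timing, and no pooled AESI count is planned

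*SAP*

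**What the plan says.** SAP 9.4 gives the counting rule: "Hypersensitivity reactions will be identified based on a preferred term of hypersensitivity within the 24 hours after completion of nebulization on any dosing day". Table footnote AE_F17b repeats it. It governs Table 14.3.2.6 for each study part and Table 14.3.2.7 for the pooled treatment groups. The pooled shell is titled "Summary of Treatment-Emergent Hypersensitivity Reactions in First 24 Hours After Completion of Nebulization by Preferred Term", although the rule admits one term and the shell has no rows for terms.

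Protocol 8.1.8.1 defines the AESI as "A suspected moderate to severe allergic/hypersensitivity reaction, including but not limited to anaphylaxis, generalized rash, edema or bronchospasm deemed possibly related to study drug". The individual stopping rule in Protocol 4.5.1 uses nearly the same words, and the dose-group stopping rule (Protocol 4.5.4, repeated in SAP 2.7) covers reactions "including but not limited to anaphylaxis, generalized rash, edema or bronchospasm possibly related to drug treatment". None of these sets a time limit.

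Both hypersensitivity tables name Listing 16.2.7.9 as their source. SAP 9.4 says of that listing: "Febrile reactions and hypersensitivity reactions within the 24 hours after completion of nebulization on any dosing day will also be listed". Its title and footnote AE_L08 agree. Its programming note 3 instead takes in onset during dosing as well as in the following 24 hours.

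AESIs are summarized by study part only (SAP 9.4, Table 14.3.2.2).

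**The concern.** A reader will take a table headed hypersensitivity reactions as the trial's count of them. Two kinds of reaction cannot enter it.

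The first is a reaction coded to a term other than 'hypersensitivity', such as anaphylaxis, rash or bronchospasm. The protocol names all three as examples.

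The second is a reaction that starts while the subject is still on the nebulizer. SAP 9.3 makes such an event treatment-emergent, since it includes events that "occur on the treatment start date with a time that is equal to or after treatment start time". For fever the SAP does cover this period in a listing: "Adverse events of pyrexia or body temperature increased during nebulization or within the 24 hours after completion of nebulization on any dosing day". Protocol 6.2.2.1 also has staff watch for bronchospasm during nebulization.

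At stake is the reported count. Table 14.3.2.6 could differ from AESI Table 14.3.2.2 for the same part, and could differ from its own source listing. The pooled active and placebo counts could be low, with no pooled AESI count beside them.

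**Working it through.** No stated figure underlies the rule, so the main check is a comparison of text.

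**1. The two definitions side by side**

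| Feature | Tables 14.3.2.6 and 14.3.2.7 | Protocol 8.1.8.1 AESI |
|---|---|---|
| Term | 'hypersensitivity' only | any; four examples given |
| Onset | 24 h after nebulization ends, on a dosing day | no limit |
| Severity | mild, moderate and severe rows | moderate to severe |
| Relationship | no condition | possibly related |

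Hypothetical events show the overlap:
- Moderate, possibly related bronchospasm 2 h after dosing: AESI, not in the tables.
- Moderate, possibly related 'hypersensitivity' during the first nebulization: AESI, not in the tables.
- Mild 'hypersensitivity' 2 h after dosing: in the tables, not an AESI.
- Moderate, possibly related 'hypersensitivity' 2 h after dosing: in both.

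The AESI is wider on term and timing and narrower on severity and causality.

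**2. Window for Listing 16.2.7.9.** SAP 9.4, the listing title and AE_L08 say after completion. Note 3 says during or after. They cannot all be followed.

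**3. Where the missing events appear by study part.** Table 14.3.2.2 and Listing 16.2.7.5 show flagged AESIs under any term. Listing 16.2.7.8 shows every AE during nebulization and up to 24 h after it. Table 14.3.1.2 shows all TEAEs.

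**4. Where they appear pooled.** The pooled overall AE summary (Table 14.3.1.1.2) has no AESI row. The listing specifications rule out study-overall listings. SAP 9.3.2 plans pooled counts by preferred term, but the Table 14.3.1.4 shell shows events only, term by term. No pooled display counts subjects with an AESI.

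**5. Dosing time before the window opens.** Inputs: 0.6 mg/mL (Protocol 6.2.2), 0.3 mL/min and number of nebulizers (Table 11), and a rest of 15 to 20 min between nebulizers (Protocol 6.2.2.1).

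Reproducing Table 11 as dose / 0.6 / 0.3 gives 22.2, 44.4, 66.7, 88.9, 111.1 and 133.3 min, against the stated 22, 44, 66, 89, 110 and 133.

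Elapsed time = stated time + (nebulizers − 1) × 15 to 20 min:

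| Dose (mg) | Nebulizing (min) | With rests (min) |
|---|---|---|
| 4 | 22 | 22 |
| 8 | 44 | 59–64 |
| 12 | 66 | 96–106 |
| 16 | 89 | 134–149 |
| 20 | 110 | 170–190 |
| 24 | 133 | 208–233 |

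Part B doses are 7 × 1,440 = 10,080 min apart, so no nebulization falls in the previous dose's 1,440 min window. Five doses leave 5 × 44 = 220 min outside at 8 mg and 5 × 110 = 550 min at 20 mg, before rests.

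In Part D, the 24 h after one daily dose covers the next nebulization if start times do not drift later. Only the first 22 min is then outside. If each start is at least 22 min later than the day before, the total is 5 × 22 = 110 min.

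**6. Weight of one uncounted subject.** At planned 3:1 numbers, pooled active is 12 + 12 + 6 = 30 and pooled placebo is 4 + 4 + 2 = 10. One subject is 100/3 = 33.3 points in a Part A or B active cohort, 100/6 = 16.7 in Part D active, 100/30 = 3.3 in pooled active and 100/10 = 10.0 in pooled placebo.

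**The case against.** The best defence is that two displays with different, footnoted definitions may give different counts without either being wrong, and that the events are visible elsewhere. Most of that stands. By part, nothing is lost. The pooled shell covers every term with no 24 h limit. With about 40 subjects, each in one part only, a reader could add up AESIs from three by-part listings. Protocol 9.4 does not itself call for a pooled active AESI count.

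On the listing conflict, a source listing may hold more than its table. The layout marks onset during nebulization, so such events would be identifiable. That limits the harm, but note 3 still contradicts the listing's own title and footnote.

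A reader might infer more than the documents support:
- That AESIs go unreported. They do not, as Table 14.3.2.2 and Listing 16.2.7.5 show.
- That the tables must always show fewer reactions than the AESI table. They can also show more, because mild and unrelated events count.
- That dose comparisons are distorted. Every dose gets the same 24 h after completion, and that comparison is sound.

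**Conclusion.** The concern holds as a minor one. The dedicated hypersensitivity tables rest on one term and a post-nebulization window that match neither the protocol's AESI nor note 3 of their own source listing. The pooled outputs lack a count of subjects with an AESI.

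The documents do not say how many events this affects, and the number may be zero. The minutes in the working show how long the uncovered period is, not any effect on results. Nebulization times are stated as targets only, and the percentage points assume the planned group sizes.

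It would be wrong to read this as a threat to stopping decisions. Those rest on the protocol's clinical criteria and PSRC review, not on these tables.

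**What to change.** 1. Add a study-overall version of AESI Table 14.3.2.2 by pooled treatment group, with an any-AESI row counting each subject once and no 24 h limit.
2. In Tables 14.3.2.6 and 14.3.2.7, keep the preferred-term row. Add a row for subjects with any AESI-flagged TEAE, whatever its onset, and a combined row counting each subject once.
3. Show onset during nebulization as its own row and keep the 24 h post-completion row for comparison across doses. In Part D, say which row takes an event that meets both.
4. Label event counts as AE records, or count AEs linked to the same dose as one reaction. Protocol 8.1 records symptoms separately when there is no diagnosis, and 8.1.1 makes a change in severity a new event, so one reaction could otherwise be counted several times.
5. Align SAP 9.4, AE_F17b, AE_L08 and note 3 to Listing 16.2.7.9 on one window, and drop 'by Preferred Term' from the hypersensitivity table titles.
6. State in a footnote whether events before protocol Version 5.0, which introduced the AESI designation, carry the flag. The documents do not show this, so it should not be assumed.

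The cost is SAP and footnote wording, light reprogramming of two tables and one listing, one extra table and a few extra rows. No new data collection is needed.

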## 9.5 Clinical Laboratory Evaluation

Baseline and all post-baseline visit values and change from baseline to post-baseline in laboratory parameters for clinical chemistry and hematology will be summarized for the safety analysis set for each study part by dose group using descriptive statistics, as described in Section 3.

C reactive protein (mg/L), white blood cell ( $\times 10^9/L$ ), and neutrophil (%) results for each subject at each visit by dose group for each study part will be provided in a line plot. An additional line plot of C reactive protein (mg/L) results for each subject at each visit by dose group will be provided for visits through Day 29 for Part A, Day 36 for Part B, and through Day 11 for Part D. Time will be represented proportionally on the x-axis.

Hematology, clinical chemistry, urinalysis, and coagulation (Part B and D) laboratory results will be presented in data listings for subjects in the safety analysis set. The listing will include the classification of low, normal, or high, the reference range, and the clinical significance. Classification of low, normal, and high laboratory values in the data listings will be based on the global laboratory reference ranges used across all sites. Clinical significance will be assessed for out of range values based on local laboratory reference ranges. Reference ranges provided in the data listings will be the global laboratory reference ranges used across all sites.

Pregnancy results will also be presented in a data listing for subjects in the safety analysis set.

## **9.6 Vital Signs, Physical Findings, and Other Observations Related to Safety**

### **9.6.1 Vital Signs**

Baseline and all post-baseline visit values and change from baseline to post-baseline values in systolic blood pressure, diastolic blood pressure, pulse rate, respiratory rate, temperature, weight, and pulse oximetry will be summarized for the safety analysis set for each study part by dose group using descriptive statistics, as described in Section 3. Height and body mass index (BMI) at baseline will be summarized for the safety analysis set for each study part by dose group using descriptive statistics, as described in Section 3.

Temperature results for each subject at each visit, through Day 7 for Part A subjects, through Day 36 for Part B subjects, and through Day 11 for Part D subjects, by study part and dose group will be provided in a line plot.

Vital sign results will be presented in a data listing for subjects in the safety analysis set.

### **9.6.2 Physical Examinations**

The number and percentage of subjects at each visit with normal, abnormal not clinically significant and abnormal clinically significant physical exam findings for each body system will be summarized for each study part by dose group for the safety analysis set.

Physical examination results will be presented in a data listing for subjects in the safety analysis set.

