2.4. Study Endpoints

2.4.1. Primary Endpoint

The safety and tolerability of nebulized MRT5005 will be assessed based on the types, frequency, and severity of treatment-emergent AEs including pulmonary exacerbations; concomitant medication use; and changes from baseline in physical examination, weight, vital signs, oxygen saturation (pulse oximetry), ECG, standard clinical laboratory tests, chest x-ray, and spirometry as a measure of pulmonary function.

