7.5.2.2. Physical Examination (Including Height and Weight)

A comprehensive physical examination or limited physical examination will be performed by the Investigator or a qualified designee at the time points described in the Schedule of Procedures.

The comprehensive physical examination will include a review of the following body systems:

- General appearance

- Skin
- Head, eyes, ears, nose, and throat
- Spine/neck/thyroid
- Musculoskeletal
- Respiratory
- Cardiovascular
- Neurological
- Abdomen (including liver, spleen, and kidneys)

The limited physical examination will be driven by any new problems or issues reported by the subject since the last clinic visit or telephone contact. At minimum, the limited physical examination will include a review of the following body systems:

- Respiratory
- Cardiovascular

Abnormalities identified during the physical examination at the initial screening visit will be documented in the subject's source documents and on the medical history CRF page. Any post-baseline new or worsening abnormalities identified after the initial physical examination should be recorded on the AE CRF page, as deemed by the Investigator.

The height and weight collected at the initial screening visit will be used to calculate the subject's body mass index (BMI) using the formula below:

$$\text{BMI} = \frac{\text{Weight [kg]}}{(\text{Height [m]})^2}$$

BMI calculated at subsequent time points will continue to use the subject's height collected at the initial screening visit.

Height should be measured in centimeters (cm) and weight should be measured in kilograms (kg). Measurements should be taken in light clothing and stocking feet (without shoes) with empty pockets. The subject's height should be recorded to the nearest centimeter and weight should be recorded to the nearest 0.1 kg.

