### **2.2 Study Endpoints**

#### **2.2.1 Primary Endpoint**

The safety and tolerability of nebulized MRT5005 will be assessed based on the types, frequency, and severity of treatment-emergent AEs including pulmonary exacerbations; concomitant medication use; and changes from baseline in physical examination, weight, vital signs, oxygen saturation (pulse oximetry), ECG, standard clinical laboratory tests, chest x-ray, and spirometry as a measure of pulmonary function.

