### **9.6.3 Other Safety Measures**

#### **9.6.3.1 *Electrocardiogram Findings***

Shifts from baseline to post-baseline visits for each study part by dose group will be presented for normal, abnormal not clinically significant and abnormal clinically significant ECG findings, as determined by investigator interpretation, for the safety analysis set. Baseline for ECG findings is defined in Section 3.

Electrocardiogram findings will be presented in a data listing for subjects in the safety analysis set.

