**Notes:**

- 1) *Include all visits where physical examination was done.*
- 2) *Include all physical examination parameters*
- 3) *Only subject with non-missing values at each visit are included in the denominators for the percentages.*
- 4) *For Part D, label Screening as Baseline*

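### Physical examination is a change-from-baseline component of the primary endpoint, but the SAP tabulates only unlinked category percentages at each visit, over denominators that can shrink at limited exams for seven of the nine body systems

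*SAP*

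**What the plan says.** Both documents place physical examination among the items judged by change. Protocol Section 2.4.1 lists "changes from baseline in physical examination, weight, vital signs, oxygen saturation" and SAP Section 2.2.1 uses the same terms.

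For the analysis, SAP Section 9.6.2 plans "The number and percentage of subjects at each visit with normal, abnormal not clinically significant and abnormal clinically significant physical exam findings", by body system, study part and dose group. The shell for Table 14.3.8.1 prints three rows (Normal; Abnormal, Not Clinically Significant, NCS; Abnormal, Clinically Significant, CS) as n/n (%) at Baseline and at each later visit. Its notes ask for every visit with an exam and every exam parameter, and set the denominator: "Only subject with non-missing values at each visit are included in the denominators for the percentages".

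ECG has the same three categories and is handled differently in SAP Section 9.6.3.1: "Shifts from baseline to post-baseline visits for each study part by dose group will be presented for normal, abnormal not clinically significant" and the two abnormal categories. Section 9.6.3.3 does the same for chest x-ray, on the same shell.

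Protocol Section 7.5.2.2 defines two exams. The comprehensive exam covers nine body systems. Of the other it says "The limited physical examination will be driven by any new problems or issues reported by" the subject, with respiratory and cardiovascular as the minimum.

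**The concern.** A percentage at each visit is not a change from baseline. It shows how many subjects sit in a category, not who moved. With three active subjects per dose group in Parts A and B and six in Part D, one subject moving each way is enough to leave a row unchanged. The study is descriptive, so these tables are the analysis. The SAP already uses the suitable method for two other assessments with the same categories and gives no reason for treating this one differently.

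The second issue is who is counted. At a limited exam, a system outside the mandatory two is examined mainly because something prompted it. Dividing by those with a result then gives a rate among subjects selected for having a problem, next to visits where everyone was examined. Limited exams are frequent: the Part A Day 1 exams; in Part B the Day 1 pre-dose exam, all post-dose exams and the next-day exams; and all ten dosing-day exams in Part D. The shell's own example, General Appearance at Day 1, is such a cell.

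**Working it through.** The plan states no figure to reproduce. The check sets the table's structure against what the endpoint needs, with small illustrations.

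**Inputs.** Group sizes from SAP Section 2.5: 3 active and 1 placebo per dose group in Parts A and B (four groups per part, so 4 pooled placebo); 6 active and 2 placebo in Part D. Categories and denominator rule from the Table 14.3.8.1 shell and notes. Body systems from Protocol Section 7.5.2.2: 9 in the comprehensive exam, 2 mandatory in the limited exam, so 9 − 2 = 7 optional.

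**1. What the planned rows identify.** For one category, count at visit − count at baseline = entries − exits. The table gives only this difference. With N = 3 and CS 1/3 at both times, entries − exits = 0. Since exits cannot exceed 1, entries are 0 or 1. Two histories print identical rows:

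| Subject | History 1 | History 2 |
|---|---|---|
| A | CS to CS | CS to Normal |
| B | Normal to Normal | Normal to CS |
| C | Normal to Normal | Normal to Normal |
| Printed, Baseline | Normal 2/3, NCS 0/3, CS 1/3 | Normal 2/3, NCS 0/3, CS 1/3 |
| Printed, visit | Normal 2/3, NCS 0/3, CS 1/3 | Normal 2/3, NCS 0/3, CS 1/3 |

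A shift table separates them: History 2 has one Normal-to-CS cell and one CS-to-Normal cell.

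**2. Where the planned table does show worsening.** Suppose A was NCS at baseline and cleared, while B went from Normal to CS. The rows become NCS 1/3 to 0/3 and CS 0/3 to 1/3, and the new CS finding is visible. Offsetting happens only within one category.

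**3. Denominator at a limited exam.** Let k be the number of subjects with a result for an optional system, with one abnormal finding. The table prints 100/k %; over all N subjects it would be 100/N %.

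| Group | N | Printed if k = 1 | Over all N |
|---|---|---|---|
| Part A or B, active dose group | 3 | 1/1 (100.0) | 1/3 (33.3) |
| Part A or B, pooled placebo | 4 | 1/1 (100.0) | 1/4 (25.0) |
| Part D, active | 6 | 1/1 (100.0) | 1/6 (16.7) |
| Part D, placebo | 2 | 1/1 (100.0) | 1/2 (50.0) |

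The case k = 1 is limiting. In a group of three, k = 2 gives 50.0% and k = 3 gives 33.3%, with no distortion. For the respiratory and cardiovascular systems k should equal the number attending, so they are unaffected.

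**4. Which baseline.** The table footnotes use the Day -1 complete exam in Parts A and B and Screening in Part D. SAP Section 3 sets a default of the last non-missing pre-dose value, with exceptions named for spirometry and ECG only. A Day 1 pre-dose limited exam exists in all three parts, so for the two mandatory systems the default would point to a different exam from the footnotes.

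**The case against.** The strongest reply is that change reaches the report by other routes. Protocol Section 7.5.2.2 sends new or worsening exam abnormalities to the adverse event page, as the investigator deems, and from there they enter the treatment-emergent event tables by part, dose group and time interval. Listing 16.2.12.1 gives every result by subject, visit and body system, and in groups of three or six a reader can follow each subject by hand. This stands and lowers the severity. It does not close the gap: the adverse event route depends on judgment, so a move from Normal to NCS may never appear there, and a listing is not a summary of a primary-endpoint component.

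It can also be said that Protocol Section 9.8.1 does not name physical examination among the assessments summarized by visit. That is correct. A reader might infer that the SAP departs from the protocol's analysis section; it does not. The mismatch is with the endpoint definition.

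Three other strong readings also fail. The table does not reduce the exam to one abnormal percentage: three categories are printed, and step 2 shows that some worsening is visible. The chest exam does not lose its denominator. And no probability of masking can be given, because the documents state no rates of baseline abnormality, new findings or clearing.

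Finally, the n/n format shows a small denominator openly, and the documents do not say how an unexamined system is coded. Both are fair. But the footnote explaining that an exam may be limited is attached to the listing, not to the table, so a reader of 1/1 is not told why.

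**Conclusion.** The point holds, at low to moderate severity. The planned summary does not deliver change from baseline for physical examination, although the endpoint calls for it and the SAP uses shift tables for ECG and chest x-ray. This follows from the table's structure and needs no assumed rates. Its reach is limited to offsetting moves within one category, and the adverse event page and the listing recover part of the information.

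The denominator point holds for the seven optional systems at limited exams. The 1/1 (100%) figure rests on two assumptions that the documents do not settle: unexamined systems are stored as missing, and only the affected subject is examined for that system. The respiratory and cardiovascular systems, which matter most for an inhaled product, are outside it.

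**What to change.** - In SAP Section 9.6.2 and Table 14.3.8.1, present a baseline-to-visit shift by body system on the existing EG_TAA shell.
- Use the exam baseline already footnoted (Day -1 complete exam in Parts A and B, Screening in Part D), and add it to the named exceptions in SAP Section 3.
- At limited-exam time points, tabulate only respiratory and cardiovascular, and leave the other seven systems to Listing 16.2.12.1. This step is needed in its own right: the ECG shell also counts only subjects with non-missing results, so the shift table alone would not cure the denominator.
- Put the limited-exam footnote from the listing on the table.

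The cost is SAP wording and reuse of a shell that already exists. The downside is a longer table with many empty cells, since nine systems and a three-by-three grid are spread over groups of three or six. Dropping the optional systems at limited exams removes some of that length. Counting all attendees for those systems would also steady the denominator, but it treats an unexamined system as not abnormal, so the listing is the safer place for them.
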